9.4.2. Confidence Interval

Consistent with the two one-sided test for bioequivalence, 90% confidence intervals will be constructed for the difference (Test (T1) – Reference (R) or Test (T2) - Test (T1)) of least square means of the log-transformed C_{max} , AUC_{0-t} and AUC_{0-inf} for BE demonstration and of the log-transformed AUC_{0-t} and C_{max} for dose proportionality. The antilog (or exponential) of these limits will give the 90% confidence interval for the ratio of geometric least square means of the test (T1) and reference (R) formulations or test (T2) and test (1) formulations.

9.4.3. Acceptance Criteria for Bioequivalence

Bioequivalence will be concluded if:

The 90% confidence interval of geometric mean ratio of log-transformed C_{max} , AUC_{0-t} and AUC_{0-inf} between test (T1) and reference (R) products fall within the range of 80.00% to 125.00% for Griseofulvin.

Dose proportionality will be concluded if:

The 90% confidence interval of geometric mean ratio of log-transformed AUC_{0-t} and C_{max} between test (T2) and test (T1) products falls within the range of 80.00% to 125.00% for Griseofulvin.

9.4.4. Accountability Procedure

9.4.4.1. Treatment of Missing Values

Missing sample values (MSV) or non-reportable values (NRV), of the plasma concentration data, will be represented as MSV and NRV in the plasma concentration tables and reasons for their missing will be documented. Any BLQ value occurring between two measurable concentration values will also be treated as missing sample (MS). These missing values will be treated as „missing values“ for Pharmacokinetic and statistical analysis. All the procedures will be performed in accordance with current version of SOP for „Calculation of Pharmacokinetic Parameters“.

For participants with missing or non-reportable concentrations for three or more of the last samples, only the C_{max} and T_{max} will be presented and included in the statistical analysis. Other PK parameters will not be reported.

Data from the participants with missing concentrations values (missed blood draws, lost samples, samples unable to be quantified) may be used if pharmacokinetic parameters can be estimated using the remaining data points. Otherwise, concentration data from these participants will be excluded from the final analysis.

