4.2. Scientific Rationale for Study Design

This is an open label, randomized, balanced, three treatment, three period, three sequence, single dose, crossover study to evaluate the bioequivalence of test Griseofulvin tablets, 500 mg versus reference Griseofulvin tablets, 500 mg as well as dose proportionality of test Griseofulvin tablets, 250 mg and 500 mg, in healthy, adult participants under fed conditions.

GSK will manufacture new GRISOVIN 500mg as well as 250mg products with SLS enhanced new formulations for better absorption. In the view of same, a three-period cross-over design was selected so that within participant comparisons can be utilized. Three-way crossover study with Test GRISOVIN 250 mg, GRISOVIN 500 mg and Reference GRISOVIN 500 (ASPEN) is selected along with Dose normalization – where GRISOVIN 250 mg single dose is given and the results are multiplied by 2.

The Pharmacokinetic (PK) sampling and washout period are designed to ensure that PK parameters are well-estimated and pre-dose concentrations are completely negligible in subsequent periods.

Sampling time points were decided based on the pharmacokinetic parameters of Griseofulvin in past successful global BE study¹⁵ and the pharmacokinetic data available in SPC⁶. The last sampling time point was selected as 96 hours (> 3 half-lives) considering the elimination half-life of around 9.5 hrs – 21 hours. The study is planned in fed condition as the SPC^{6, 15} of griseofulvin recommends it's intake with food. BE study conforms to CDSCO and/or other global regulatory guidelines.

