7.2. Participant Discontinuation/Withdrawal from the Study

- A participant may withdraw from the study at any time at his/her own request or may be withdrawn at any time at the discretion of the investigator for safety, behavioral, compliance or administrative reasons. This is expected to be uncommon.
- If participant is found positive for breath alcohol test in any ambulatory visit, then the ambulatory sample of that particular visit will not be collected. However, he/she may be requested to come for subsequent ambulatory samples in same study period, if continuation in the study is not expected to have any significant impact on the safety or PK outcome in the judgement of Investigator.
- The decision to withdraw the subject if suffering from vomiting/diarrhoea (3 or more consecutive watery stools) at or before two times of median T_{max} (8 hours) will be taken by the Investigator considering the nature and amount of vomitus, likely/anticipated impact on the study outcome and the participants' health status.
- If participant is dropped out due to personal reasons in a given period, he can be continued in subsequent periods if the PK data generated through such participation can be used for statistical analysis.
- At the time of discontinuing from the study, if possible, an early discontinuation visit should be conducted, as shown in the SoA. See SoA for data to be collected at the time of study discontinuation and follow-up and for any further evaluations that need to be completed.
- The participant will be permanently discontinued both from the study treatment and from the study at that time.
- If the participant withdraws consent for disclosure of future information, the sponsor may retain and continue to use any data collected before such a withdrawal of consent.
- If a participant withdraws from the study, he/she may request destruction of any samples taken and not tested, and the investigator must document this in the site study records.

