8.5. Pharmacokinetics

Whole blood samples of approximately 5 mL will be collected for measurement of plasma concentrations of Griseofulvin as specified in the SoA.

An intravenous cannula will be inserted into the participant's arm for the collection of the blood samples before the pre-dose blood sample and up to 24.00 hrs post-dose. If difficulties occur in blood withdrawal or if the participant is not feeling comfortable with the cannula, then the cannula will be removed before 24.00 hrs post-dose and the remaining blood samples will be collected through fresh vein puncture or by recannulation. When meals, vitals and sample collections coincide, samples will be collected first followed by vitals and then meal will be served.

Before every blood sample collection, 0.2 mL of blood present in the intravenous cannula will be discarded during the use of the intravenous cannula except for the ambulatory sample. Also after every blood sample collection, 0.2 mL of heparinised saline (by mixing 1 mL of 5000 IU/5mL of heparin with 500 mL of normal saline) will be injected into the intravenous cannula.

Twenty-Two (22) blood samples will be collected in Na-Heparin vacutainers at pre-dose (collected within 01.00 hour prior to dosing), 00.50, 01.00, 01.50, 02.00, 02.50, 03.00, 03.50, 04.00, 04.50, 05.00, 05.50, 06.00, 06.50, 07.00, 08.00, 10.00, 12.00, 24.00, 48.00, 72.00 and 96.00 hours post dose.

Note: The actual time of blood collection (24 hour clock) will be considered for calculation of PK parameters. Duration of 2 minutes is required for the completion of procedure of blood sample collection. Hence, the reason for deviation up to 2 minutes for the blood sample collection activity need not be documented. However, the reason for delay beyond 2 minutes will be documented in the case record form and/or other document.

Blood samples after 24 hrs will be collected on ambulatory basis through direct vein puncture. The actual end-point time of collection of each blood sample will be recorded in the CRF.

Ambulatory blood sample will be collected up to 04.00 hrs from the scheduled time of blood sample collection. If the participant reports for blood sample collection beyond 04.00 hrs, the blood sample will not be collected, and the participant will be requested to come for the next ambulatory sample (if any).

Approximate blood loss during the study:

		Males	Females
Total PK blood samples (66 x 5 mL)	:	330 mL	330 mL
Pre study screening	:	Upto 10 mL	Upto10 mL

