If the 90% confidence interval of geometric mean ratio of C_{\max} , AUC_{0-t} and AUC_{0-inf} between test (T1) and reference (R) products falls within the range of 80.00% to 125.00% for Griseofulvin, the null hypothesis will be rejected. In this case the test product (T1) will be concluded as bioequivalent to the reference product R.

If bioequivalence is demonstrated between the Test product (T1) and reference product (R), the following step II will be followed.

Step 2: For dose proportionality (T2 vs. T1):

Dose normalization will be done for test product T2 for AUC_{0-t} and C_{\max} parameter by multiplying with the correction factor 2.

PROC MIXED procedure will be used for analysis of variance and the estimation of least square mean differences (Test (T2) - Test (T1)) of the test (T2) and test (T1) products on the log-transformed pharmacokinetic parameter AUC_{0-t} and C_{\max} . The corresponding standard errors of the differences will also be computed. Based on these parameters, the 90% confidence intervals will be constructed for the least square mean differences of log-transformed parameter AUC_{0-t} and C_{\max} . The antilog (or exponential) of the limits obtained from the log-transformed data will give the 90% confidence interval for the ratio of geometric means of test (T2) and test (T1) products.

Null hypothesis will be rejected if the 90% confidence interval of geometric mean ratio of AUC_{0-t} and C_{\max} between test (T2) and test (T1) products falls within the range of 80.00% to 125.00% for Griseofulvin.

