9.3. Populations for Analyses

Three (3) populations sets are defined for analysis purposes.

Safety Analysis Set

The safety population will include all randomized participants who receive at least one dose of study medication. The safety population will be used for all analyses of safety data. Individual pharmacokinetic parameters and its descriptive statistics will be presented.

BE Analysis Set

The data of subjects completing at least 2 periods with 500mg test and 500mg reference treatments of the study will be subjected to statistical analysis.

Dose Proportionality Analysis Set

The data of subjects completing at least 2 periods with 500mg test and 250mg test treatments will be subjected to dose proportionality analysis.

The following populations are defined:

Population	Description
Enrolled	All participants who signed the ICF
Randomized	All participants assigned to study treatment.
BE Analysis Set	The data of subjects, completing at least 2 periods with 500mg test and 500mg reference treatments of the study will be subjected to statistical analysis.
Safety Analysis Set	The safety population will include all randomized participants who receive at least one dose of study medication. The safety population will be used for all analyses of safety data. Individual pharmacokinetic parameters and its descriptive statistics will be presented
Dose Proportionality	The data of subjects completing at least 2 periods with 500mg

Analysis Set	test and 250mg test treatments will be subjected to dose proportionality analysis
--------------	---

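### Does keeping AUC(0-t) when both the 72 h and 96 h samples are missing distort the bioequivalence or dose-proportionality test?

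*Protocol*

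**What the plan says.** Under protocol section 9.4.4.1, Cmax and Tmax are the only parameters kept "For participants with missing or non-reportable concentrations for three or more of the last samples". With fewer samples missing, the data "may be used if pharmacokinetic parameters can be estimated using the remaining data points". SAP section 10.5.2 repeats both rules. Protocol section 8.5 and SAP section 8.1.1.2 end AUC(0-t) at the final quantifiable concentration. It is calculated separately for each participant and product, and neither document sets a common end time.

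The last three scheduled samples are at 48, 72 and 96 h. A participant who stays in the study can miss one in two ways:

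- Late arrival (protocol section 8.5): "If the participant reports for blood sample collection beyond 04.00 hrs, the blood sample will not be collected".
- A positive breath alcohol test (protocol section 7.2): "then the ambulatory sample of that particular visit will not be collected". Later samples in that period may still be taken "if continuation in the study is not expected to have any significant impact on the safety or PK outcome".

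Protocol section 4.2 explains the sampling length: "The last sampling time point was selected as 96 hours (> 3 half-lives) considering the elimination half-life".

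AUC(0-t) is a primary endpoint for both comparisons. AUC(0-inf) is primary for T1 versus R only. Dose proportionality has its own analysis set in section 9.3 ("The data of subjects completing at least 2 periods with 500mg test and 250mg test treatments will be subjected to dose proportionality analysis") and is reached only through the gate in section 9.1: "If bioequivalence is demonstrated between the Test product (T1) and reference product (R), the following step II will be followed".

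**The concern.** Losing the 72 h and 96 h samples is a loss of two, so the three-sample rule does not apply. The within-participant contrast can then set exposure over 48 h against exposure over 96 h, and part of the difference has nothing to do with the formulation. A 48 h window also falls short of the protocol's own justification of more than three half-lives whenever the half-life is 16 h or longer.

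If the losses fell mainly on one product, the geometric mean ratio would be biased. That could cost power, or push a truly inequivalent ratio inside the limits. T2 versus T1 looks the more exposed comparison, because it has no AUC(0-inf) criterion to restore the missing tail.

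**Working it through.** **Inputs.** Protocol section 9.2: true ratio 0.95, within-subject CV 21%, 27 evaluable, 36 enrolled. Section 9.4.3: limits 80.00% to 125.00%. Section 2.2: half-life 9.5 to 21 h, peak by 4 h and held for 10 to 20 h. Section 8.5: sampling times. The documents give no rate of missed late samples and no quantification limit, so the loss rates and profile shapes below are assumptions.

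**1. The plan's own figure.** Within-subject SD on the log scale = √ln(1 + 0.21²) = 0.2077. Standard error = 0.2077 × √(2/27) = 0.0565. Power of the two one-sided tests is 0.904 with 25 df (two-treatment fit) or 0.911 with 50 df (three-treatment fit). The stated 90% is reproduced.

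**2. Half-lives covered** (window ÷ half-life, for 9.5 / 15 / 21 h).

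- 96 h: 10.1 / 6.4 / 4.6
- 72 h: 7.6 / 4.8 / 3.4
- 48 h: 5.1 / 3.2 / 2.3, reaching 3 at 48/3 = 16 h

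A 72 h window still exceeds three half-lives throughout the range.

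**3. Loss for one affected value** (linear trapezoids at the protocol times, 9.5 / 15 / 21 h).

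| Profile | AUC(0-48)/AUC(0-96) | AUC(0-72)/AUC(0-96) |
|---|---|---|
| One-compartment, Tmax 4 h | 0.961 / 0.889 / 0.818 | 0.994 / 0.973 / 0.943 |
| Peak held to 20 h | 0.935 / 0.855 / 0.784 | 0.990 / 0.964 / 0.933 |

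So a 48 h cut lowers the value by about 4% to 22%, and a 72 h cut by about 1% to 7%.

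**4. Effect on the study ratio if every cut falls on one product.** Multiplier = r^(m/27), where r is the 48 h/96 h ratio and m the number of participants affected. With r = 0.818, m = 1 gives 0.9926 and m = 3 gives 0.9779. With r = 0.784, m = 1 gives 0.9910.

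**5. Loss unrelated to product.** If a fraction p is cut in each product, the expected shift cancels. The variance of the log difference rises by 2p(1 − p)(ln r)². At p = 0.10 and r = 0.818 this is 2 × 0.10 × 0.90 × 0.2009² = 0.0073, on a base of 2 × 0.04316 = 0.0863. The standard error therefore rises by a factor of √1.084 = 1.041. Simulated results at n = 27, one-compartment profile:

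| Half-lives | No loss | 5% per product | 10% per product |
|---|---|---|---|
| All 21 h | 0.904 | 0.894 | 0.882 |
| Spread evenly, 9.5 to 21 h | 0.904 | 0.899 | 0.895 |

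Type I error stays between 4.8% and 5.1% in my check of the balanced cases. A 72 h cut changes power by at most 0.002. The harshest shape (r = 0.784 for everyone, 10% loss) gives power of about 0.87. At n = 36, power is 0.96 with no loss and about 0.95 with 10% loss at r = 0.818.

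**6. Loss confined to one product.** With 10% cut in one product, none in the other and n = 27, type I error for AUC(0-t) alone is 7.5% (half-lives spread) or 9.4% (all 21 h). A larger n does not cure this: at n = 36 the all-21 h case is about 10%. For T2 versus T1, adding the AUC(0-t) gate from Step 1 gives 5.0% to 9.3%, for true T1/R of 0.95 to 1.05. If loss is random at 2%, 5% or 10% per period, the chance that at least 3 of 27 are cut in a named product and none in the other is about 0.9%, 3.8% or 3.0%.

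**The case for a change.** The case for a change is that the gap is plain in the text, the plan itself creates routes to it, and the safeguards make a cut profile visible without saying what to do. SAP section 10.8.2 lists the last time used for Kel and the residual area. Section 10.8.4 lists actual time points. Section 10.3.2 promises to assess major timing deviations, and section 8.1.4.1 asks for well-defined profiles. In an open-label study, a permissive rule leaves some discretion over a primary endpoint. A short paragraph cutting both periods to the last time sampled in both would hold power at 0.901 to 0.905 and type I error at 4.9% to 5.0% in simulation.

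The gap stands, and so does the greater exposure of T2 versus T1. The remedy is less clear-cut:

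- It would also apply when only the 96 h sample is missing, where it gains almost nothing and discards a valid 96 h value from the other period.
- T1 could carry two different AUC(0-t) values, one for each comparison.
- It requires two-treatment models. If protocol section 9.4.1 means a three-treatment fit, power drops from 0.911 to 0.904 even when nothing is missing. That 0.7 points is similar to the 0.5 to 0.9 points regained with spread half-lives (0.904 − 0.899 and 0.904 − 0.895).
- It would impose on both periods the same 48 h window that was criticised as too short.

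The discretion is also bounded. SAP section 10.5.2 requires every exclusion to be documented with its reason, and the bioanalyst is blinded to sequence. Protocol section 9.4.4.1 defers to an SOP on PK calculation that is not among the documents and may already cover the case.

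**Conclusion.** The wording does allow a 48 h AUC(0-t) to be compared with a 96 h one, but the plan followed as written still gives a sound conclusion. Lateness and a positive alcohol test are not linked to a product in the documents, and each participant is planned to receive all three. Under loss unrelated to product, type I error is unaffected. At n = 27 power falls by about 2 points at an assumed 10% loss with a one-compartment profile and every half-life at 21 h (0.904 to 0.882), and by 1 point or less at 5%. The harshest plateau shape at 10% costs about 3 points. A participant who misses two ambulatory draws is not a dropout, so the margin from enrolling 36 is still available.

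The inflated type I errors depend on a one-sided loss that nothing in the documents suggests. A statistician who meets such a profile can see it in the planned listings and show its influence with a sensitivity analysis, leaving the standard AUC(0-t) definition and the planned model alone. The judgement would change if late-sample loss proved frequent and clearly uneven between products.

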9.4.4.2. Missing samples

Missing samples can be due to withdrawal of participant and accidental spillage of samples as mentioned in current version of SOP for „Missing Sample“.

9.4.4.3. Treatment of outliers

Before the results of the bioequivalence analysis are summarized into confidence intervals, the available untransformed C_{max} , AUC_{0-t} and AUC_{0-inf} data for BE demonstration and AUC_{0-t} and C_{max} data for dose proportionality will be tested for possible outliers based on studentized residuals. Participants identified as outliers will be removed regardless of whether results meet the standard

Values that meet both of the following criteria will be considered outliers:

- Studentized residual value larger than 3; and
- Observation outside of the range $[Q1 - 3 \times IQR; Q3 + 3 \times IQR]$, where Q1, Q3 and IQR are respectively the 1st quartile, the 3rd quartile and the inter-quartile range of the distribution of all observations (i.e. regardless of the formulation).

Data from participants who meet both criteria for C_{max} , AUC_{0-t} and AUC_{0-inf} data for BE demonstration and AUC_{0-t} and C_{max} data for dose proportionality will be excluded from the statistical analysis for the outlying period.

No more than 5% of the participants may be considered outliers. If greater than 5% of the participants are considered outliers, no data will be removed from the statistical analysis.

A valid clinical or physiological reason will be explored for such an outlier, if found, and will be reported if identified by the Principal Investigator of the study (in accordance with current SOP of statistical outlier).

However, to avoid the biasness in the results, the statistical analysis will be performed on both the data sets i.e. including as well as excluding the outliers if the outlier is justified clinically as well.

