9.4.1. Analysis of Variance

Step 1: For BE Demonstration (T1 vs. R):

ANOVA will be performed using PROC MIXED on log-transformed pharmacokinetics parameters C_{\max} , AUC_{0-t} and AUC_{0-inf} at α level of 0.05.

The analysis of variance model will include sequences, period and treatment as fixed factors and participants nested within sequence as random factor [i.e. Model LC_{\max} or $LAUC_{0-t}$ or $LAUC_{0-inf}$ = sequence period treatment (fixed factors) and random: Participant (Sequence) (random factor)].

A separate ANOVA model will be used to analyze each of the parameters. All main effects will be tested against the residual error (mean square error) from the ANOVA model as the error term.

Each analysis of variance will also include calculation of least-square means, adjusted differences between formulation means and the standard error associated with these differences.

Step 2: For dose proportionality (T2 vs. T1):

ANOVA will be performed using PROC MIXED on log-transformed pharmacokinetics parameter AUC_{0-t} and C_{\max} at the α level of 0.05.

The analysis of variance model will include sequences, period and treatment as fixed factors and participants nested within sequence as random factor [i.e. Model $LAUC_{0-t}$ or LC_{\max} = sequence period treatment (fixed factors) and random: Participant (Sequence) (random factor)].

A separate ANOVA model will be used to analyze each of the parameters. All main effects will be tested against the residual error (mean square error) from the ANOVA model as the error term.

Each analysis of variance will also include calculation of least-square means, adjusted differences between formulation means and the standard error associated with these differences.

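### The outlier rule screens raw-scale values for log-scale analyses, falls almost only on high values, and contradicts itself on whether removal needs a clinical cause

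*Protocol*

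**What the plan says.** Protocol 9.4.4.3 sets the timing and scale: "Before the results of the bioequivalence analysis are summarized into confidence intervals, the available untransformed" Cmax and AUC values are screened, for bioequivalence and for dose proportionality. A value is an outlier if its studentized residual exceeds 3 and it also lies beyond 3 interquartile ranges from the quartiles of all observations, formulations pooled.

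The section then says four things about the consequence:
- "Participants identified as outliers will be removed regardless of whether results meet the standard".
- Data meeting both criteria "will be excluded from the statistical analysis for the outlying period".
- "If greater than 5% of the participants are considered outliers, no data will be removed from the statistical analysis".
- A clinical or physiological reason is to be explored, under a CRO procedure for statistical outliers. To avoid bias, the analysis is to be run on both data sets, "including as well as excluding the outliers if the outlier is justified clinically as well".

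The primary analysis uses another scale. Protocol 9.4.1: "ANOVA will be performed using PROC MIXED on log-transformed pharmacokinetics parameters". Protocol 9.4.3 judges success on this: "The 90% confidence interval of geometric mean ratio of log-transformed" parameters, against 80.00% to 125.00%.

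SAP 10.5.2 only requires exclusions to be documented with a reason. SAP 2.1 declares no change from the protocol's analysis.

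**The concern.** PK parameters are analysed on the log scale because their distribution is right-skewed. A raw-scale screen treats part of that ordinary right tail as aberrant and is nearly blind to the left tail. A valid high value can therefore leave the primary confidence interval on numerical grounds alone, while an equally extreme low value stays in.

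If a formulation occasionally gives very high exposure, that is information a bioequivalence study should keep or explain. It is also unclear whether a result including the deleted value would be reported when no cause is found. That is the case in which a reader most needs it.

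**Working it through.** **Inputs.** From Protocol 9.2: 27 evaluable participants (9 per sequence), 36 randomized, within-subject CV 21%, ratio 0.95, limits 80% to 125%. No between-subject CV is given, so it is assumed and varied.

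**The plan's own figure.** Within-subject log-SD = sqrt(ln(1 + 0.21²)) = 0.2077. SE = 0.2077 × sqrt(2/27) = 0.0565. Exact two one-sided tests power is 91.1% with 50 residual df (all three treatments in the model) and 90.3% with 24 (T1 and R only). The stated 90% is reproduced.

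**Lower fence.** Q1 − 3(Q3 − Q1) = 4Q1 − 3Q3, which is negative when Q3/Q1 > 4/3. For log-normal data Q3/Q1 = exp(2 × 0.6745 × SD), so the threshold is SD = ln(4/3)/1.349 = 0.2133, a total CV of 21.6%. Given 0.2077 within subject, the between-subject log-SD needed is sqrt(0.2133² − 0.2077²) = 0.048, a CV of 4.8%.

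| Between-subject CV | Total log-SD | Lower fence / median | Upper fence / median |
|---|---|---|---|
| 5% | 0.214 | −0.002 | 2.02 |
| 10% | 0.230 | −0.08 | 2.11 |
| 20% | 0.287 | −0.35 | 2.38 |
| 30% | 0.360 | −0.69 | 2.74 |

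These are population values. In simulated samples of 27 the fence is negative in 44-45% of trials at CV 5%, 94-97% at 20%, and at least 99.5% at 30%.

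**What is flagged** (simulation, taking the absolute residual):
- One 4-fold-high value is flagged in 86-100% of trials at between-subject CV 5-30%; one quarter-size value in at most 1.5%.
- A near-zero value (2% of expected) is flagged in 35% of trials at CV 5% and 21% at CV 10%. At about 20% or more, low values are almost never flagged.

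**Direction.** One value of 27 wrong by a factor of 3 shifts the log ratio by about ln(3)/27 = 0.041. In simulation, deleting a tripled R value raised T1/R by about 4%, and deleting a tripled T1 value lowered it by about 4%.

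**Cap.** 5% of 27 is 1.35 and of 36 is 1.8. One outlying participant (3.7% or 2.8%) is removed; with two (7.4% or 5.6%) nothing is.

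**Clean data.** The BE Analysis Set takes subjects "completing at least 2 periods with 500mg test and 500mg reference treatments of the study", but the plan does not say whether T2 values enter the T1 vs R model, so both fits were run (n = 27, between-subject CV 30-60%).

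| | T1 and R only | All three |
|---|---|---|
| Rise in type I error at 1.25 (points) | 0.3-0.5 | 0.2-0.3 |
| Valid value deleted, one parameter suffices | 5-22% | 10-28% |
| Valid value deleted, all three must be outlying | 0.5-9% | 1-13% |

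Power at 0.95 is essentially unchanged.

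**Illustration, no basis in the documents.** 4% of T1 periods have 4-fold exposure and the true geometric mean ratio is exactly 1.25, so the uncontaminated ratio is 1.25/4^0.04 = 1.183. False bioequivalence on one parameter:
- T1 and R only: 8.5% with all data, 13.7-16.1% under the rule.
- All three: 8.9-9.0% with all data, 13.5-16.5% under the rule. Repeat runs reached 17.6%.
- Mirror case (quarter exposure, ratio 0.80): 8.9-9.5% with all data, 9.2-10.0% under the rule.
- Other settings at 1.25: 2% of periods at 2-fold, about 6% to 6-7%; 8% at 4-fold, 9-11% to 17-22%.

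**The case against.** The rule is pre-specified and does not depend on the outcome. The clause about removal regardless of the result protects against selective deletion and is not the fault. The 5% cap limits the damage, and clean-data operating characteristics barely move. All of this stands.

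The last sentence may also be kinder than it looks. If its condition attaches only to excluding, the all-data analysis always runs and exclusion needs a clinical reason. A reader might infer that an unexplained deletion will certainly have no with-outlier result. The documents do not establish that: the sentence supports either reading, and the cited CRO procedure is not available. But the kinder reading contradicts the earlier sentence ordering removal, so the text still needs repair.

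A reader might also infer that the rule cannot delete a low value. That is too strong. If the absolute residual is meant and between-subject CV is low, near-zero values are sometimes flagged. Nor does the rule necessarily favour the new product, because a high reference value is as removable as a high test value.

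Other safeguards are partial. Protocol 7.2 and 8.5 can remove some poor profiles for cause. SAP 8.1.4.1 plans residual plots for the log-scale model but attaches no outlier rule. Individual parameters are tabulated (SAP 10.8.2), so an outsider could rerun the analysis, but the SAP does not commit to doing so.

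Finally, the contamination scenario is invented, and the all-data analysis already exceeds 5% there because its model is violated. It shows a mechanism and does not forecast a result.

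**Conclusion.** The point holds and should be fixed. Three faults rest on the text alone: the screening scale does not match the analysis scale, the removal sentence requires no cause, and the last sentence conflicts with it. The SAP resolves none of them.

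That the rule falls almost wholly on high values depends on the unstated between-subject CV. It is firm from about 20% upward and less complete at 5-10%. The bias has no fixed direction.

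The expected effect on clean data is small; the main cost there is the needless loss of a valid value in some trials. A material effect on the bioequivalence conclusion needs occasional extreme exposure, which the documents neither assert nor exclude.

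Two ambiguities are secondary: whether the participant or only the period is removed (at most 0.2 points on pass rates in the three-treatment fit), and whether one parameter or all must be outlying.

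**What to change.** In Protocol 9.4.4.3, carried into SAP 10.5.2:

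1. Keep all valid observations in the primary bioequivalence and dose-proportionality analyses.
2. Exclude a value only for a documented cause, established without reference to treatment or to the bioequivalence result, and apply this whether or not the criteria are met.
3. Flag outliers by absolute studentized residual above 3 from the log-scale model, separately for each parameter.
4. Always report the analysis without flagged values, as a sensitivity analysis.
5. Replace the conflicting removal and clinical-justification sentences. The 5% cap then has no function and can go.

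The cost is wording and one sensitivity run. The downside is that an aberrant value with no identified cause stays in the primary confidence interval and may widen it.
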